Target Population:	Patients planning to undergo bilateral Photorefractive Keratectomy (PRK) surgery.
TREATMENT(S)	

Study Drug	DEXTENZA (dexamethasone ophthalmic insert) 0.4 mg for intracanalicular use
Dose/Route/Schedule:	All patients will be enrolled for bilateral PRK surgery. The first eye will be randomized to Group A or B; the second eye will be selected for the opposite group. Group A will receive Dextenza at the time of PRK surgery while Group B will receive prednisolone acetate 1% QID 1 week, BID 1 week following bilateral PRK surgery. All eyes will receive topical moxifloxacin QID for 1 week. Moxifloxacin is used post-op regardless of the research.
ENDPOINT(s)	
Primary:	Adapted COMTOL Survey
Secondary:	Percentage of eyes epithelialized at POD 4 Corneal Staining Corneal haze Ocular Pain Assessment Uncorrected distance visual acuity Corrected distance visual acuity Manifest refraction spherical equivalent Modified SPEED questionnaire
Safety:	IOP spikes (increase of 10 mm Hg or greater than baseline) Adverse events

TABLE OF CONTENTS

Clinical Study Protocol Synopsis	2
List of Tables	5
1. Introduction and Rationale	6
1.1 Introduction	6
1.2 Rationale.....	6
1.2.1 Rationale for Study Design	7
2. Study endpoints	7
2.1 Primary Endpoint.....	7
2.2 Secondary Endpoints	7
2.3 Safety Endpoints.....	8
3. Study Design.....	8
3.1 Study Description and Duration	8
4. Selection, Withdrawal, and Replacement of Patients.....	8
4.1 Study Population	8
4.1.1 Inclusion Criteria.....	8
4.1.2 Exclusion Criteria.....	9
4.2 Treatment Logistics and Accountability	9
4.2.1 Packaging, Labeling, and Storage	9
4.2.2 Supply and Disposition of Treatments	10
4.2.3 Treatment Accountability.....	10
4.3 Concomitant Medications and Procedures	10
5. Study Schedule of Events and Visit Descriptions	10
5.1 Schedule of Events	10
5.2 Study Visit Descriptions	11
5.2.1 Study Procedures.....	11
5.2.2 Unscheduled Visits.....	14
5.2.3 Adverse Event Information Collection.....	14
5.3 Rescue Criteria.....	15
6. Safety Definitions, Reporting, and Monitoring.....	15
6.1 Definitions	15
6.1.1 Adverse Event	15

6.1.2	Serious Adverse Event	15
6.2	Recording and Reporting Adverse Events	16
7.	Study Variables.....	16
7.1	Demographic and Baseline Characteristics	16
8.	Ethical and Regulatory Considerations.....	16
8.1	Good Clinical Practice Statement.....	16
8.2	Informed Consent	16
8.3	Patient Confidentiality and Data Protection	17
8.4	Institutional Review Board	17

LIST OF TABLES

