1.2.1 Rationale for Study Design

This prospective contralateral eye study will compare the outcomes of 20 patients undergoing bilateral PRK. In one eye the patient will receive a topical steroid and the contralateral eye will receive a Dextenza ophthalmic insert. Both eyes will receive a topical antibiotic.

The primary endpoint of patient preference and pain was chosen based on previous studies that have shown decreasing topical medications increases patient satisfaction. Secondary endpoints including SPEED survey and corneal staining were chosen to test the hypothesis of less ocular surface disease with Dextenza. Time to epithelialization will be studied to see the positive or neutral effects of steroid plus punctal occlusion on epithelialization. Finally, the other secondary endpoints are standard measures for PRK.

The study inclusion and exclusion criteria were chosen based on patients who normally would be successful with laser refractive surgery. The study follow-up visits were based on the Vance Thompson Vision standard post-operative follow-up protocols.

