2.2 Secondary Endpoints

To determine at Post-Operative Day 3 and 4:

- Percentage of eyes epithelialized at Day 3 and Day 4.

To determine through Month 1 (Day 28 +/- 3 days):

- Mean pain score per eye (Group A vs. Group B) as measured by the Numerical Rating Scale (NRS) at Day 3, Day 4, Week 2 (collected via telephone survey), and Month 1.
- Patient preference as measured by a modified SPEED questionnaire at Pre-op Visit and Month 1.

To determine through Month 3 (+/- 4 days):

- Incidence and grade of post-operative corneal haze as measured by Heidelberg Anterior Segment OCT at Pre-op Visit, Month 1, and Month 3.
- Post-operative corneal staining score as measured by the National Eye Institute (NEI) grading system at Day 3, Day 4, Month 1, and Month 3.

- Uncorrected visual acuity as measured by ETDRS chart at 4m at Month 1 and Month 3.
- Best-corrected visual acuity as measured by ETDRS chart at 4m at Month 1 and Month 3
- Manifest Refraction Spherical Equivalent as measured by the Optometrist at Month 1 and Month 3.

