4.1.1 Inclusion Criteria

A patient's study eye must meet the following criteria to be eligible for inclusion in the study:

- Any adult patient who is planned to undergo bilateral PRK surgery.
- Willing and able to comply with clinic visits and study related procedures
- Willing and able to sign the informed consent form

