4.1.2 Exclusion Criteria

A patient who meets any of the following criteria will be excluded from the study:

- Patients under the age of 18.
- Patients who are pregnant (must be ruled out in women of child-bearing age with pregnancy test).
- Active infectious ocular or systemic disease.
- Patients with active infectious ocular or extraocular disease.
- Patients actively treated with local or systemic immunosuppression including systemic corticosteroids.
- Patients with known hypersensitivity to Dexamethasone.
- Patients with severe disease that warrants critical attention, deemed unsafe for the study by the investigator.
- Patients with a history of ocular inflammation or macular edema.
- Patients with allergy or inability to receive intracameral antibiotic.
- Patients on systemic non-steroidal anti-inflammatory drugs (NSAID) greater than 1,200 mg/day
- Patients with a corticosteroid implant (i.e. Ozurdex).
- Patient with corneal pathology which pre-disposes them to unsatisfactory outcomes.
- Patients who do not have 20/20 snellen visual acuity potential pre-operatively.
- MRSE greater than 6 diopters.
- Greater than 2 diopters anisometropia.

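### Different planned refractive targets in a patient's two eyes are neither excluded nor recorded, so they would add noise to the paired UDVA and MRSE comparisons

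*Protocol*

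**What the plan says.** The design is a within-patient comparison. Section 1.2.1 states: "This prospective contralateral eye study will compare the outcomes of 20 patients undergoing bilateral PRK". On allocation, the treatment entry of the synopsis says: "The first eye will be randomized to Group A or B; the second eye will be selected for the opposite group". Section 3.1 describes the same scheme.

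Two secondary endpoints in Section 2.2 depend on where the surgeon aims each eye: "Uncorrected visual acuity as measured by ETDRS chart at 4m at Month 1 and Month 3" and "Manifest Refraction Spherical Equivalent as measured by the Optometrist at Month 1 and Month 3". Neither refers to an intended refraction.

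Eligibility in Section 4.1.1 is broad: "Any adult patient who is planned to undergo bilateral PRK surgery". The refractive and acuity exclusions in Section 4.1.2 are "MRSE greater than 6 diopters", "Greater than 2 diopters anisometropia" and "Patients who do not have 20/20 snellen visual acuity potential pre-operatively". None of them mentions the planned post-operative refraction.

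Table 1 and the visit lists in Section 5.2.1 collect manifest refraction at screening, Day 28 and Month 3. They do not collect the target of either eye at any visit.

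**The concern.** Pairing the eyes removes what they share, such as age, healing and habits. It does not remove what differs between them by plan. An adult scheduled for one distance eye and one near eye meets the listed criteria. After surgery the near eye will have a more myopic MRSE and worse uncorrected acuity at 4 m, whichever steroid it received. That planned gap enters the patient's Group A minus Group B difference in full.

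The entry limits do not prevent this. Two eyes with the same refraction before surgery can be given different targets, and 20/20 potential says nothing about the uncorrected distance vision being aimed for. Even if the anisometropia limit were read as covering the target, 2 D would still admit a planned 1.5 D difference.

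At stake is the precision of two secondary comparisons, in a trial whose introduction and rationale (Sections 1.1 and 1.2) raise the possibility of better refractive and visual outcomes with the insert.

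**Working it through.** The protocol gives no power calculation, SD or effect size for UDVA or MRSE, so there is no stated figure to reproduce.

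**From the protocol:** n = 20 pairs; within each patient one eye goes to each group by randomizing the first eye.

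**Assumed for illustration:**
- k patients have a planned between-eye difference D. The main case is k = 4, D = 1.5 D.
- Each near-target eye falls in either group with probability 1/2, independently across patients.
- The SD of the paired MRSE difference without unequal targets is 0.3 or 0.5 D.
- The true effect for the power figures is 0.25 D, with a two-sided 5% paired t-test.
- A near target costs 0.4 logMAR of UDVA (range 0.3 to 0.5), and one letter is 0.02 logMAR.

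**1. Expected shift.** Each affected patient contributes +D or −D with equal probability, so the expected shift in the mean difference is 0 for any k and D.

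**2. Chance shift in mean MRSE difference.** SD = D√k / n.
- One affected patient moves the mean by 1.5/20 = 0.075 D.
- k = 4: SD = 1.5 × 2/20 = 0.15 D. The largest shift is 1.5 × 4/20 = 0.30 D, reached when all four near eyes fall in one group. That has probability 2 × 0.5⁴ = 0.125.
- k = 2: largest shift 1.5 × 2/20 = 0.15 D.
- k = 6: SD = 1.5 × √6/20 = 0.18 D and largest shift 0.45 D. A shift of at least 0.25 D needs five or six near eyes on one side, probability 2 × (6 + 1)/64 = 0.22.

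**3. SD of the paired difference.** √(s² + (k/n)D²).
- s = 0.3, k = 4: √(0.09 + 0.2 × 2.25) = √0.54 ≈ 0.73 D.
- s = 0.5, k = 4: √(0.25 + 0.45) = √0.70 ≈ 0.84 D.

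**4. Test behaviour** (simulation, 40,000 runs per scenario, 20 pairs, D = 1.5 D):

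| SD without unequal targets | k | Type I error | Power at 0.25 D |
|---|---|---|---|
| 0.3 D | 0 | 0.050 | 94% |
| 0.3 D | 2 | 0.038 | 46% |
| 0.3 D | 4 | 0.052 | 29% |
| 0.5 D | 0 | 0.050 | 57% |
| 0.5 D | 2 | 0.047 | 34% |
| 0.5 D | 4 | 0.049 | 24% |

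Type I error is not inflated; power falls.

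**5. UDVA.** One affected patient moves the mean by 0.4/20 = 0.02 logMAR, or 1 letter (range 0.015 to 0.025). For k = 4 the chance SD is 0.4 × 2/20 = 0.04 logMAR, or 2 letters (0.03 to 0.05). The largest shift is 0.08 logMAR, or 4 letters (0.06 to 0.10), again with probability 12.5%.

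**6. Effect of the fix on MRSE.** If achieved MRSE equals target plus error in each eye, then achieved minus intended leaves only the error. The planned difference cancels, and the SD returns to 0.3 or 0.5 D.

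**The case against.** Four points can be made in the protocol's defence.

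- **Randomization protects the contrast.** This stands. A reader might infer that a planned difference would be counted as an effect of the steroid. The documents do not support that: the eye is randomized, the expected shift is zero, and a paired analysis carries the extra spread in its standard error.
- **The summary of MRSE may be left to the SAP, which is not shown.** This stands in part. A reader might also infer that signed means will be compared, so that hyperopic and myopic misses cancel. Section 2.2 prescribes no such summary; it names a measurement, an assessor and two visits. But an SAP cannot build a deviation from target, or pick out pairs with both eyes set for distance, from a variable the visit schedule does not collect. Eligibility and data collection belong to the protocol.
- **No passage says that patients with unequal targets will be enrolled.** This is true, and it makes the size conditional. Nothing rules them out either.
- **The scope is narrow.** This is also true. The point does not reach the primary endpoint, the adapted COMTOL survey. Best-corrected acuity, measured at the same visits, does not depend on the target.

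**Conclusion.** The point holds as a matter of precision. Unequal planned targets are not excluded, not recorded and not reflected in how UDVA and MRSE are defined. If such patients enrol, the two paired comparisons become noisier, and with 20 pairs a visible chance imbalance is possible. With 4 patients at 1.5 D, both assumed, that imbalance could reach 0.30 D in mean MRSE difference with probability 12.5%, and power for an assumed 0.25 D effect would drop from 94% to 29% or from 57% to 24%. With one such patient the shift is 0.075 D; with none there is no effect.

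The conclusion of no systematic shift assumes 1:1 randomization and that each eye's target is chosen without regard to its group. This is a low-cost improvement to two secondary endpoints and does not threaten the trial's main conclusion.

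**What to change.** Make three changes:

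1. Add the intended post-operative spherical equivalent of each eye to Visit 1 in Table 1 and Section 5.2.1. Enter it before the randomization result is known, since both fall at Visit 1 and treatment is open-label.
2. In Section 2.2, define the MRSE endpoint as achieved minus intended spherical equivalent for each eye.
3. In Section 2.2, state that UDVA is compared in patients with both eyes targeted for distance. Because the target is fixed before allocation, this restriction leaves the randomized comparison intact.

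The cost is one extra data field, which the surgical plan should already supply, and possibly a few pairs left out of the UDVA comparison. If 4 of 20 were left out, the standard error for a given SD would rise by a factor of √(20/16) ≈ 1.12. No patient need be turned away, and the MRSE comparison keeps all 20 pairs.

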2.3 Safety Endpoints

To determine through Month 3 (+/- 4 days):

- Incidence of increased IOP >10 mmHg above baseline at all timepoints
- Occurrence of adverse events at all timepoints

3. STUDY DESIGN

3.1 Study Description and Duration

This prospective, open-label, single-center, randomized, investigator-sponsored clinical study seeks to investigate the outcomes of patients undergoing bilateral PRK surgery with the treatment of a dexamethasone intracanalicular insert compared to topical standard of care steroid. All eyes will receive treatment. Additionally, all eyes will receive topical moxifloxacin QID for 1 week. Moxifloxacin is used post-op regardless of the research.

Twenty patient eyes undergoing bilateral PRK surgery will be randomized to receive either Dextenza (Group A) OR standard of care prednisolone acetate 1% QID for 1 week, BID for 1 week (Group B). The contralateral eye will receive treatment with either Dextenza or topical prednisolone as a comparator based on randomization of first eye to Group A or Group B. Post-operative evaluations to be performed on Day 3, Day 4, phone call survey at Week 2, Month 1, and Month 3.

4. SELECTION, WITHDRAWAL, AND REPLACEMENT OF PATIENTS

4.1 Study Population

The study aims to enroll 20 patients planning to undergo bilateral PRK surgery.

4.1.1 Inclusion Criteria

A patient's study eye must meet the following criteria to be eligible for inclusion in the study:

- Any adult patient who is planned to undergo bilateral PRK surgery.
- Willing and able to comply with clinic visits and study related procedures
- Willing and able to sign the informed consent form

4.1.2 Exclusion Criteria

A patient who meets any of the following criteria will be excluded from the study:

- Patients under the age of 18.
- Patients who are pregnant (must be ruled out in women of child-bearing age with pregnancy test).
- Active infectious ocular or systemic disease.
- Patients with active infectious ocular or extraocular disease.
- Patients actively treated with local or systemic immunosuppression including systemic corticosteroids.
- Patients with known hypersensitivity to Dexamethasone.
- Patients with severe disease that warrants critical attention, deemed unsafe for the study by the investigator.
- Patients with a history of ocular inflammation or macular edema.
- Patients with allergy or inability to receive intracameral antibiotic.
- Patients on systemic non-steroidal anti-inflammatory drugs (NSAID) greater than 1,200 mg/day
- Patients with a corticosteroid implant (i.e. Ozurdex).
- Patient with corneal pathology which pre-disposes them to unsatisfactory outcomes.
- Patients who do not have 20/20 snellen visual acuity potential pre-operatively.
- MRSE greater than 6 diopters.
- Greater than 2 diopters anisometropia.

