4.2 Treatment Logistics and Accountability

4.2.1 Packaging, Labeling, and Storage

Intracanalicular dexamethasone insert must be stored in a secure area accessible only to the Investigator and their designee(s) and refrigerated and stored between 2° C and 8° C. Intracanalicular dexamethasone insert contains 0.4 mg dexamethasone and is designed to provide a sustained and tapered release of therapeutic levels of dexamethasone to the ocular surface for up to 30 days for the reduction of post-surgical inflammation and pain associated with ocular surgery. Dexamethasone is an anti-inflammatory 9-fluoro-glucocorticoid (also termed a glucocorticoid agonist) and is the active ingredient found in MAXIDEX® 0.1% (dexamethasone ophthalmic suspension), which contains approximately 50 µg of dexamethasone per drop.

Study inserts will be supplied by Ocular Therapeutix in a sealed foil pouch containing one intracanalicular dexamethasone insert in a foam carrier.

Study inserts will be shipped to the site via overnight shipping using cold packs to maintain a temperature of 2° to 8° C. The Investigator, or an approved representative (e.g. pharmacist), will ensure that all study drug

inserts are stored in a secured area, under recommended storage conditions and in accordance with applicable regulatory requirements. The shipping box is to be opened and stored immediately at the site in a refrigerator intended for investigational products at a temperature of 2° to 8°C.

When the insert is removed from the refrigerator, it should be visually inspected. Exposure of the insert to temperatures outside these limits is not recommended. Records of actual storage conditions (i.e. temperature log) at the study site must be maintained; and must include a record of the dates, when the refrigerator was checked, the initials of person checking, and the temperature.

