4.3 Concomitant Medications and Procedures

At the discretion of their physician, patients may continue to receive all medications and standard treatments administered for other conditions.

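### Eligibility and concomitant-medication rules do not address eye-pressure history or IOP-lowering treatment, although an IOP rise is the only specifically named safety event

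*Protocol*

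**What the plan says.** **Safety endpoints.** Section 2.3 of the protocol has two items: "Incidence of increased IOP >10 mmHg above baseline at all timepoints" and "Occurrence of adverse events at all timepoints". The synopsis has the same pair: "IOP spikes (increase of 10 mm Hg or greater than baseline) Adverse events". The IOP rise is thus the only event singled out by name.

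**Exposure.** Section 1.2.1 states: "In one eye the patient will receive a topical steroid and the contralateral eye will receive a Dextenza ophthalmic insert". Section 4.2.1 describes the insert as giving "sustained and tapered release of therapeutic levels of dexamethasone to the ocular surface for up to 30 days". In the synopsis and section 3.1 the comparator is two weeks of prednisolone acetate drops.

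**Eligibility.** Section 4.1.1 admits "Any adult patient who is planned to undergo bilateral PRK surgery", subject to consent and compliance. Section 4.1.2 lists 15 exclusions. The one on past ocular disease is "Patients with a history of ocular inflammation or macular edema".

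**Concomitant treatment.** Under section 4.3, at their physician's discretion, "patients may continue to receive all medications and standard treatments administered for other conditions".

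**Measurement.** Table 1 schedules IOP at screening, Day 3, Day 4, Day 28 and Month 3. Day 14 is a telephone call without IOP. The screening value is tied to no eligibility limit.

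**The concern.** A patient with glaucoma, ocular hypertension or a known pressure response to steroids can meet every written criterion, receive a steroid in both eyes, and stay on IOP-lowering treatment. Two things are at stake.

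- **Patient safety.** The protocol treats an IOP rise as the event worth naming, but does not say whether the patients most prone to it should take part. The decision is left unwritten.
- **Endpoint sensitivity.** An eye on IOP-lowering treatment is less likely to cross a threshold of about 10 mmHg above baseline. The same holds for an eye whose rise is found and treated between scheduled measurements: it may read as unremarkable at the next one, and section 2.3 does not say how to count it.

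Eligibility and permitted treatment are protocol matters, so a separate SAP would not be expected to supply the first part.

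**Working it through.** The plan gives no figure on this point, so there is none to reproduce. The check is a comparison of sections, followed by arithmetic for scale only.

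**Step 1: does any exclusion in 4.1.2 reach pressure?** By subject, the 15 exclusions are:

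- age; pregnancy; infectious disease (two overlapping bullets);
- immunosuppression, including systemic corticosteroids; dexamethasone hypersensitivity; an existing corticosteroid implant;
- severe disease judged unsafe by the investigator;
- past ocular inflammation or macular edema; corneal pathology;
- allergy to, or inability to receive, intracameral antibiotic; systemic NSAID dose;
- visual acuity potential; refractive error; anisometropia.

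None names glaucoma, ocular hypertension, a baseline IOP, a previous steroid pressure response or IOP-lowering treatment. Three steroid-related bullets cover hypersensitivity, an existing implant and current systemic use; none covers pressure history.

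**Step 2: does another section close the gap?** Section 1.2.1 says the criteria were chosen around patients expected to do well with laser refractive surgery; pressure risk is not given as a basis. The severe-disease bullet is discretionary and does not naturally cover controlled ocular hypertension or a past steroid response. Section 4.3 makes no exception for IOP-lowering drugs. The gap stays open.

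**Step 3: how long is IOP unobserved?** From Day 4 to Day 28 is 28 − 4 = 24 days, or 21 to 27 days with the ±3-day window. The drop course (1 week + 1 week = 14 days) begins and ends before the Day 28 measurement, and the insert releases for up to 30 days. Much of the steroid exposure in both groups therefore falls where no IOP is scheduled.

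**Step 4: scale.** With 20 patients there are 20 eyes per group, so one eye is 1/20 = 5 percentage points of a group's incidence. Zero events in 20 eyes still has a one-sided 95% upper bound of 1 − 0.05^(1/20) = 13.9%.

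The protocol does not give the share q of candidates with a relevant pressure history. Treating q as an assumption, the chance of enrolling at least one such patient is 1 − (1 − q)^20:

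| Assumed q | Expected number in 20 (20q) | Chance of at least one |
|---|---|---|
| 1% | 0.2 | 1 − 0.99^20 = 18% |
| 2% | 0.4 | 1 − 0.98^20 = 33% |
| 5% | 1.0 | 1 − 0.95^20 = 64% |
| 10% | 2.0 | 1 − 0.90^20 = 88% |

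These are chances of enrolment, not of an IOP event.

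**The case against.** **No passage contradicts another, and broad entry can be a virtue.** True: an open population makes safety results more general. But the protocol does not say that such patients are included on purpose. It is silent about them while naming the event to which they are most prone.

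**A reader might infer that IOP-lowering treatment confounds insert against drops.** The documents do not support that for treatment in place at entry. The endpoint is a change from baseline, so an eye on stable treatment has a treated reference value. The first eye is randomized and the other takes the opposite group, so a pre-treated eye falls to either group by chance. Treatment of both eyes, or a steroid-response history, is shared within the pair. What remains is noise and lost sensitivity. Treatment started after surgery is different: it could depend on the group, and an entry criterion does not deal with it.

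**A reader might take the percentages above as the size of the harm.** They rest on assumed prevalences. Nor does one such patient by itself move a group by 5 points: that needs an event in that eye, and if both eyes rise, both groups move 5 points and the difference is zero. Responders would add events and treated eyes would remove them; the net direction is unknown.

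**Screening and recording already help.** Visit 1 takes history, medications and IOP, with slit-lamp and fundus examination, and concomitant medications are recorded at every clinic visit. A careful surgeon may well screen such patients out, and IOP-lowering treatment would appear in the record. This lessens the concern, but nothing written guarantees exclusion, and section 2.3 has no rule for using the medication record. Adverse-event capture is an uncertain backstop, since section 6.2 limits recording to medically relevant events.

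**A counting rule may belong in the SAP.** Fair. If an SAP already has one, that half of the fix is met. The eligibility half is not.

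**Conclusion.** The omission is real and worth correcting. Pressure-related history and current IOP-lowering treatment are unaddressed in 4.1.2, and 4.3 lets such treatment continue, in a trial that gives a steroid to both eyes and names one specific safety event, an IOP rise. At-risk patients can be enrolled, and treated eyes are less likely to register the event.

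It is a patient-safety and endpoint-sensitivity point. It does not show a biased group comparison, and its size cannot be derived from the protocol. The 5 points per eye and the enrolment chances show only that in a trial this small one patient can matter.

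Two assumptions carry the conclusion. The link between steroid exposure and the IOP endpoint is inferred from both study treatments being steroids; the protocol does not call the event steroid-related. That treatment would mask a rise follows from what 4.3 permits and is not an outcome the protocol describes.

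**What to change.** 1. **Sections 4.1.2 and 4.3.** Reconcile both with the IOP endpoint. The investigator should state in 4.1.2 how glaucoma, ocular hypertension, a known steroid pressure response and current IOP-lowering treatment affect eligibility, and make 4.3 agree. Which rule to adopt is a clinical decision and is not proposed here. The history, medication list and IOP from Visit 1 suffice to apply it.
2. **Section 2.3.** Count as an IOP event, or report separately by group, any eye in which IOP-lowering treatment is started after surgery, so that a rise treated between Day 4 and Day 28 is not lost. Separate reporting keeps the threshold-based count intact.
3. **In the same edit,** reconcile the threshold: the synopsis includes a rise of exactly 10 mmHg and section 2.3 does not.

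The cost is one amendment and no new procedure. The downsides are an occasional screen failure and, if started treatment is counted as an event, some treated rises below the stated threshold in the total.
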